7.1 Specification of Safety Parameters

Potential study participants will be screened at the Baseline visit, prior to randomization, using several laboratory and physiologic measures. These measures will be used to screen out subjects with potentially serious diagnosed or undiagnosed medical or psychiatric conditions.

Laboratory measures:

Study participants must be within normal ranges (or the value must be determined as "not clinically significant" by a study clinician) on several blood tests, including comprehensive metabolic panel (CMP) and complete blood count (CBC).

Abnormal and clinically significant ECGs will be sent to the cardiologist at the Clinical Heart Center in the Department of Cardiology at UT Southwestern for interpretation and recommendations. Based on the information received from the cardiologist, the participant may be excluded or discontinued from the study.

If clinically indicated by the PI, a physical examination will be performed to exclude those with potentially serious undiagnosed clinical findings.

An MRI screening form will be completed by a participant and reviewed by an MRI technologist prior to each scan to exclude participants with any metal objects in their body or any medical conditions precluding a scan.

Psychiatric measures:

To exclude participants with clinically significant severe depressive symptoms potential participants with a baseline HRSD score > 27 will be excluded. Participants who have failed 2 or more adequate antidepressant trials (defined as 4 or more weeks at a therapeutic dose) will also be excluded.

7.2 Methods and Timing for Assessing, Recording, and Analyzing Safety Parameters

Blood draw for CMP and CBC will be performed at Baseline and Visit 6. ECG will be done at Baseline, Visit 2, Visit 4, and Visit 6. Vital signs will be collected at Baseline and at each MRI scan. Urine pregnancy test (UPT) will be done at Baseline. If clinically

indicated, physical examination performed by a study clinician will be done at Baseline and Visit 6. An MRI screening form will be completed prior to each scan. A COVID-19 safety screener mandated by UT Southwestern will be done within 24-48 hours of each in-person visit.

In past two clinical trials (n=70 at 100 mg/day and n=80 at 500 mg/day) of pregnenolone in patients with Bipolar Disorder (BPD) or Major Depressive Disorder (MDD), no difference in side effect burden, as evaluated with a self-report side effect scale that assesses a variety of somatic symptoms, was observed with pregnenolone as compared to placebo. No adverse events classified as likely related to pregnenolone were observed in either study.

A clinical trial by Marx et al. in patients with schizophrenia (n=21) administered pregnenolone at the same dose as the current study (500 mg) and also reported excellent safety and tolerability in combination with psychotropic medications.(3) The only reported side effects with pregnenolone were mild restlessness, mild muscle pain or stiffness, and mild coldness in the extremities. No changes in TSH or blood glucose levels were observed with pregnenolone. Total cholesterol and LDL levels significantly decreased with pregnenolone, but the levels were not obtained in the fasting state. No ECG changes were observed. Lipids will be collected as part of the CMP panel to see if a reduction in LDL and total cholesterol can be replicated. ECG will be obtained as a precautionary measure, although changes are not anticipated. The GABAergic pregnenolone metabolite allopregnanolone has a benzodiazepine-like effect on sleep.(11) However, pregnenolone administration at the dosages that have been studied in humans do not appear to be associated with sedation or somnolence. Nonetheless, these symptoms will be monitored through both side effect and depressive symptom scales. There are no known drug-to-drug interactions with pregnenolone or its metabolites.

Further evidence of the safety and tolerability of pregnenolone comes from a study of 120 patients (n=38 women) with schizophrenia receiving 500 mg of pregnenolone or placebo for eight weeks.(3) The number of participants experiencing treatment-emergent adverse events was comparable between the placebo and pregnenolone groups (58% vs. 55%, respectively). Moderate-intensity adverse events were reported by 8.3% of participants in the placebo group and 13.3% of participants in the pregnenolone group. No participants in either group reported adverse events of severe intensity. Three participants in the pregnenolone group and none in the placebo group had serious adverse events (SAEs); no SAEs were related to pregnenolone. Study medication was discontinued in only one participant (secondary to reasons unrelated to study drug).

Studies of pregnenolone for arthritis from the 1950s provide longer-term and higher-dose safety data. McGavack gave pregnenolone with doses ranging from 400-1000 mg/day for a duration, in some cases, longer than one year with good safety and

tolerability.(19) Freeman et. al. also gave pregnenolone doses of 700-800 mg/day for up to 30 weeks with good tolerability.(20)

As mentioned above, pregnenolone appears to increase levels of progesterone. Marx et al. reported a mean increase in progesterone from 0.38±0.15 ng/ml to 2.17±0.64 ng/ml in patients with schizophrenia given pregnenolone for eight weeks at the dose proposed in the current application.(3) Eight of these nine participants were men. Thus, the impact of pregnenolone on progesterone in women is not well studied. The mean progesterone level achieved during pregnenolone administration in this study was higher than is typical for men (0.3-1.2 ng/ml), postmenopausal women (<0.7 ng/ml), or premenopausal women during the follicular phase (0.2-1.2 ng/ml), but was lower than during the luteal phase (3.3-25.0 mg/ml). Oral contraceptives containing the combination of progestin (a synthetic progesterone) AND estradiol were shown in the Women's Health Initiative, following several years of treatment, to increase the risk of deep vein thrombosis, pulmonary embolism, myocardial infarction, breast cancer, and dementia in postmenopausal women.(21) Therefore, this study excludes persons at an elevated risk, based on personal, and also excludes women over 65 years of age.

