The approximate duration of study participation for an individual participant will be 9 weeks with additional 2 weeks reserved for unforeseen scheduling events. All participants will be given pregnenolone (2 x 250 mg or 2 x 400 mg capsules) and placebo at some point during the study (depending on the order of randomization). Oral encapsulated pregnenolone and placebo will be prepared by the Abrams Royal Compounding Pharmacy and distributed to the investigator by the pharmacy staff. The laboratory of [name] at Duke University will perform the neurosteroid assays.

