6.2.2 Enrollment, Baseline, and/or Randomization

Enrollment

UT Southwestern IRB considers a participant "enrolled" in the study once they sign an IRB-approved written informed consent. This study will use the same definition of enrollment, and consider participants enrolled in the study once they sign an informed consent at the Baseline visit. Participants are unable to complete any Baseline assessments to determine study eligibility until they sign an informed consent, per UT Southwestern policy.

Baseline Assessments

Baseline assessments to determine eligibility (see Section 4 for criteria) will include. In order to maintain safety precautions during COVID-19 pandemic, all assessments may be done virtually (with exception of vital signs, ECG, urine pregnancy and drug screens, and blood draws):

- Informed Consent Form
- Demographics (self-report)
- Structured Clinical Interview Clinician Version (SCID-CV) for DSM 5
- Psychiatric Evaluation performed by a study clinician*
- Medical History*

- Physical Examination* (only if clinically indicated in PI judgement; Epic medical record review will be used to collect medical history information).
- Concomitant Medications
- Urine Pregnancy Test & Drug Screen (UPT will be done only for women without a permanent method of birth control, such as hysterectomy or bilateral tubal ligation)
- Vital Signs (temperature, blood pressure, heart rate, respiratory rate, weight)
- Electrocardiogram (ECG)
- Blood Chemistry (Comprehensive Metabolic Panel with lipids, Complete Blood Count with differential)
- Blood Chemistry (neurosteroid levels: pregnenolone, allopregnanolone, pregNANolone, androsterone)
- Hamilton Rating Scale for Depression (HRSD, clinician-rated)
- Systematic Assessment for Treatment Emergent Events (SAFTEE, self-report)
- Columbia-Suicide Severity Rating Scale (C-SSRS, clinician-rated)
- UCLA Loneliness Scale, Version 3 (UCLA, self-report)

*These assessments may be performed at the second part of Baseline or at Visit 1 depending on clinician and participant schedule.

Other procedures performed in the study:

- Neuroimaging (Visit 2, 4, 6)
 - o Structrual MRI scan (6 min)
 - o Phase contrast (PC) MRI (30 seconds)
 - o Resting State Functional MRI (5.5 min)
 - o ¹HMRS data acquisition (17 min)

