The MRI scan should fall on the last day of the study medication dose. In the event that MRI needs to be rescheduled or scheduled for a later date (within the allowable visit window), participants will be instructed on when to take the first medication dose to ensure that the 7th day dose falls on the day of the MRI scan.

Randomization (Visit 1)

If a participant meets all the inclusion criteria and does not meet any of the exclusion criteria at Baseline, as well as indicates willingness to participate in follow-up visits, she will be considered eligible for randomization, and will receive the first treatment course within 14 days of the Baseline visit (at Visit 1). If the Baseline visit needs to be split into two different visits due to scheduling constraints, then the 14-day window will be counted from the second part of the Baseline. A participant will be considered randomized and active in study once they receive the first course of treatment at Visit 1. Depending on the status of COVID-19 pandemic, Visit 1 may be performed remotely using virtual meeting platforms or in person. If Visit 1 occurs remotely, then the investigational drug will be mailed to the participant upon completion of the visit.

If a participant does not come back for Visit 1 within 14 days of Baseline, or is ineligible based on the inclusion/exclusion criteria, then they will be considered a screen fail and not randomized. A participant who does not come back for Visit 1 will be eligible for a rescreening at a future date (at least 30 days from the original Baseline visit). However, a participant who is considered a screen fail based on the inclusion/exclusion criteria will not be eligible for a rescreening.

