6.2.4 Followup Visits

Baseline visit (~ 3 hours):

- Consent 30 minutes
- Structured Clinical Interview for DSM 5, Clinician Version (SCID CV) to establish psychiatric diagnosis for inclusion purposes - 1 hour
- Psychiatric evaluation and physical exam performed by a study clinician 30 minutes
- Safety assessments: HRSD, SAFTEE, C-SSRS (described in detail in the assessments section) - 30 minutes
- Self-report: UCLA 5 minutes
- Blood work, vital signs, ECG, urine pregnancy test and drug screen 30 minutes

Psychiatric evaluation and medical history may be postponed until Visit 1 depending on clinician availability and participant schedule. Baseline visit may be split in two visits to accommodate participant schedule.

In order to maintain safety precautions during COVID-19 pandemic, all Baseline assessments may be done virtually (with exception of vital signs, ECG, urine pregnancy and drug screens, and blood draws).

Visit 1 (~ 40 minutes). Depending on the status of COVID-19, Visit 1 may be conducted virtually (to maintain safety precautions) or in person:

- Physician follow-up (includes review of concomitant medications and adverse events) – 20 minutes
- Safety assessments: HRSD 15 minutes
- At this visit (or within the allowable visit window) (and Visits 3 and 5), participants will begin a 7 day course of pregnenolone 500 mg, pregnenolone 800 mg, or placebo, which will be administered in a double-blind, crossover method. This means that all participants will receive a 7 day exposure to each dose of pregnenolone and placebo throughout the study (each exposure will begin at Visit 1, 3, and 5); however, the order of treatment administration will be random. Each 7-day treatment administration will be followed by a 14 day washout period. (Example order: 800 mg x 7 days; washout x 14 days; placebo x 7 days; washout x 14 days; 500 mg x 7 days). If the visit is conducted remotely, the investigational drug will be mailed to the participant.

Visit 1 must take place within 30 days from the Baseline visit in order for a participant to be randomized into the study. If necessary, Baseline visit may be split in two visits in order to accommodate participant scheduling and decrease participant burden. In the case 30 day window will be counted from the time of the second part of Baseline.

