Maximum time allowed between Visit 1 and Visit 2: 14 days (allow +/-3 day window for rescheduling). Participants will be instructed on when to begin their medication, such that the last dose (7th day) of the medication falls on the day of the MRI scan.

Visit 2 (~ 2.5 hours):

- Physician follow-up (includes review of concomitant medications and adverse events) – 20 minutes (done virtually or in person)
- Safety assessments: HRSD, SAFTEE, C-SSRS 30 minutes (done virtually or in person)
- Self-report: UCLA 5 minutes (done virtually or in person)
- Blood work for neurosteroid levels, vital signs, ECG 30 minutes
- MRI scan 1 hour

Maximum time between Visit 2 and Visit 3: 21 days (allow +/-5 day window for rescheduling)

Visit 3 (~ 40 minutes). Depending on the status of COVID-19, Visit 1 may be conducted virtually (to maintain safety precautions) or in person:

- Physician follow-up (includes review of concomitant medications and adverse events) – 20 minutes
- Safety assessments: HRSD 15 minutes
- At this visit (or within the allowable visit window) (and Visits 3 and 5), participants will begin a 7 day course of pregnenolone 500 mg, pregnenolone 800 mg, or placebo, which will be administered in a double-blind, crossover method. This

means that all participants will receive a 7 day exposure to each dose of pregnenolone and placebo throughout the study (each exposure will begin at Visit 1, 3, and 5); however, the order of treatment administration will be random. Each 7-day treatment administration will be followed by a 14 day washout period. (Example order: 800 mg x 7 days; washout x 14 days; placebo x 7 days; washout x 14 days; 500 mg x 7 days). If the visit is conducted remotely, the investigational drug will be mailed to the participant.

Maximum time between Visit 3 and Visit 4: 14 days (allow +/-3 day window for rescheduling). Participants will be instructed on when to begin their medication, such that the last dose (7th day) of the medication falls on the day of the MRI scan.

Visit 4 (~ 2.5 hours):

- Physician follow-up (includes review of concomitant medications and adverse events) – 20 minutes (done virtually or in person)
- Safety assessments: HRSD, SAFTEE, C-SSRS 30 minutes (done virtually or in person)
- Self-report: UCLA 5 minutes (done virtually or in person)
- Blood work for neurosteroid levels, vital signs, ECG 30 minutes
- MRI scan 1 hour

Maximum time between Visit 4 and Visit 5: 21 days (allow +/-5 day window for rescheduling)

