All participants will be required to have a negative pregnancy test prior to the study enrollment. In the event of an unexpected pregnancy, the study participation will be discontinued and the appropriate referrals will be provided to the participant. . Participants will be provided with contact information to the UT Southwestern and Parkland Hospital OBGYN clinics, as well as additional local resources as needed. If a participant elects to continue pregnancy, and with participant permission, she will be contacted at 3 month intervals (months 3, 6, and 9) to check the status of pregnancy, as well as at 3 months post-partum to collect information on pregnancy outcome. The pregnancy and the follow-up plan for the participant will be reported to the DSMB and NCCIH within 48 hours of PI awareness. The pregnancy will be reported to the UT Southwestern IRB if it also meets criteria for UPIRSO and requires a modification to the protocol.

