8. INTERVENTION DISCONTINUATION

Study intervention may be discontinued for participants for any of the following reasons:

- Development of any exclusion criteria for the study while participating in the study (e.g., development of severe MDD).
- Development of active suicidal or homicidal ideation with plan and intent, clear and progressive worsening of psychiatric symptoms that in the opinion of the investigator makes continued care within the research study unsafe.
- Development of psychotic features (hallucinations, delusions, disorganized thoughts)
- Development of severe or life-threatening medical condition, pregnancy or psychiatric hospitalization.
- Withdrawal of informed consent by the participant.
- Opinion of the investigator that continued participation is unsafe or unwise.
- Participants who start psychotropic medications during the trial will be withdrawn from the study. Because the study has a short observation period and a crossover design we suggest that this is both a practical and scientifically justified

approach.

Participants will continue to be followed with their permission if study intervention is discontinued. Participants discontinued prior to Visit 6 will be asked to return for a Safety Visit. Participants who meet discontinuation criteria at Visit 6 will return for the regularly scheduled Safety Visit within 14 days of study discontinuation.

At the Safety Visit, assessments will be given based on their clinical relevance to the discontinuation criteria met by the study participant, in addition to a doctor visit, routine vital signs, AE review, and side effects scales. Clinically significant abnormal labs will be repeated at the Safety Visit, if necessary, and participants will continue to be followed until safety concerns are adequately resolved and appropriate referrals have been made.

Study participants may choose, at any time, to stop participating in the study. In the event that a participant chooses to do so, the study intervention will be stopped and the participant will be asked to return for a Safety Visit as outlined above.

Due to the short length of each treatment exposure (7 days), no temporary discontinuations will be allowed. In the event of participant discontinuation, no further evaluations will be performed for outcomes, only the safety measures as indicated above.

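### The urine pregnancy test is scheduled only at Baseline and not repeated before any of the three drug courses, so it is nominally at least 40 to 42 days old at course 3; separately, 6.2.2 and 6.2.4 give inconsistent Baseline-to-Visit 1 limits (14 and 30 days).

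*Combined protocol and SAP*

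**What the plan says.** **Pregnancy testing.** Section 7.2 reads: "Urine pregnancy test (UPT) will be done at Baseline". The synopsis diagram, the 6.1 schedule, and sections 6.2.2 and 6.2.4 also place the test at Baseline. The procedure lists for Visits 1 to 6 and the Safety Visit contain none. Section 7.4 asks for one negative result: "All participants will be required to have a negative pregnancy test prior to the study enrollment". Section 6.2.2 limits who is tested: "UPT will be done only for women without a permanent method of birth control". The opening of section 7 names the test among the safety measures used while women are on the intervention, but gives no further time point.

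**Drug release.** Courses start at Visits 1, 3 and 5, which 6.1 labels as remote. These visits list clinician follow-up (concomitant medication and adverse events) and the HRSD. Section 6.2.4 adds: "If the visit is conducted remotely, the investigational drug will be mailed to the participant".

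**Other safeguards.** Pregnancy is an exclusion in 4.2. Section 8 allows discontinuation for "Development of any exclusion criteria for the study while participating in the study" and also names pregnancy itself. Section 7 requests contraception and has a clinician monitor risks at every visit. Sections 7.1 and 7.2 require an MRI screening form before each scan.

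**Baseline-to-Visit 1 limit.** Section 6.2.2 sets the screen-fail rule: "If a participant does not come back for Visit 1 within 14 days of Baseline", a woman is not randomised, and she may be rescreened no sooner than 30 days after the original Baseline. Section 6.2.4 instead makes Visit 1 within 30 days of Baseline the condition for randomisation.

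**The concern.** Section 7 treats harm to an embryo or fetus as a listed risk, and 4.2 and section 8 treat pregnancy as a bar to receiving the drug. With one test at the start, those rules act after Baseline only once a pregnancy has become known. A woman who conceives after Baseline and has not noticed can begin a 7-day course with the plan followed exactly. The plan gives no pregnancy safety data at 500 or 800 mg/d, and 7.2 acknowledges that the drug's effect on progesterone in women is not well studied.

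The second matter is separate and smaller. The two limits determine who is randomised, and they do not agree for a woman who returns in the third or fourth week.

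**Working it through.** **Inputs.** Course of 7 days and washout of 14 days (6.2.4). Scan on the day of the seventh dose, that is, 6 days after the first dose (6.2.2). Baseline-to-Visit 1 gap of up to 14 days (6.2.2) or 30 days (6.2.4). Sample size 31.

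**The plan's own figure.** Section 3 states: "The approximate duration of study participation for an individual participant will be 9 weeks with additional 2 weeks reserved for unforeseen scheduling events". Three cycles give 3 × (7 + 14) = 63 days = 9 weeks, so the nominal cycle reproduces the stated length. That count runs from Visit 1 to the Safety Visit.

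**Nominal age of the test.** One cycle is 7 + 14 = 21 days, or 6 + 14 = 20 days if the washout is counted from the day of the last dose. Age at the start of course k = gap + (k − 1) × cycle.

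| Gap (days) | Course 1 | Course 2 | Course 3 |
|---|---|---|---|
| 0 | 0 | 20–21 | 40–42 |
| 14 | 14 | 34–35 | 54–56 |
| 30 | 30 | 50–51 | 70–72 |

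The first row is the floor for courses 2 and 3: test and first dose on the same day, with a full 14-day washout. The rescheduling tolerance does not shorten the washout as written, because the 5 days attach to a 21-day maximum (21 − 5 = 16, still at least 14).

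**These are not upper bounds.** Section 6.2.4 permits longer intervals: "Maximum time allowed between Visit 1 and Visit 2: 14 days (allow +/-3 day window for rescheduling"), with the same limit from Visit 3 to Visit 4, and 21 days (± 5) from Visit 2 to 3 and from Visit 4 to 5.

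- Visit 1 to Visit 5 at the maxima: 2 × (14 + 21) = 70 days. Visit 5 then falls on day 14 + 70 = 84 or 30 + 70 = 100 from Baseline.
- With the tolerances: 2 × (17 + 26) = 86 days, giving day 100 or 116.
- Dosing is timed back from the scan, so the first dose can fall 14 − 6 = 8 days after the visit, or 17 − 6 = 11 with the tolerance.
- Both Baseline windows run from the second part of a split Baseline. A test done at the first part would be older still.

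**The two Visit 1 limits.** Days with inconsistent status: 30 − 15 + 1 = 16 (days 15 to 30). The split-Baseline provision does not explain the difference, because both sections use it. Nominal length from Baseline: 14 + 63 = 77 days or 30 + 63 = 93 days. The stated 9 + 2 weeks is 77 days.

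**The case against.** The strongest reply is that the plan already has several layers: a Baseline test, an exclusion, requested contraception, clinician risk review at every visit, an MRI form before every scan, a discontinuation rule, and pregnancy follow-up in 7.4. Women with a permanent contraceptive method are not affected, each exposure lasts only 7 days, and the documents set no testing frequency that this schedule breaches. How often to retest is partly a judgement.

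Most of that is fair, and it rules out calling the plan unprotected. It does not close the gap. An interview finds a pregnancy that the woman knows or suspects. The MRI form's questions are not shown, and it is completed at a scan meant to fall on the last dosing day, after most of that course has been taken. The wording at the start of section 7 suggests an intent to test during treatment, but no visit carries it out.

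A reader might also infer three stronger things that the documents do not support.

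- *That staff cannot comply with both Visit 1 limits.* The 30-day text is a ceiling and does not order anyone to be randomised. Applying 14 days satisfies both sections, though the 30-day text then has no function.
- *That the 9 + 2 weeks cap the age of the test.* Section 3 calls that duration approximate, and the visit maxima exceed it.
- *That some number of exposed pregnancies can be expected.* The number of women able to conceive among the 31 is not given, so no such figure can be derived.

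**Conclusion.** Both parts stand, as two separate points.

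1. No pregnancy test is scheduled after Baseline. At course 3 the only result is at least 40 to 42 days old, nominally 54 to 56 days after a 14-day gap and 70 to 72 after a 30-day gap, and it can be older at the permitted visit maxima. This assumes a full 14-day washout, and it concerns only women without permanent contraception. It is a participant-safety gap that should be closed because the remedy is cheap.
2. The status of a return on days 15 to 30 is inconsistent between 6.2.2 and 6.2.4. This is a wording correction and adds no weight to the first point.

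Neither affects the sample size, the primary endpoints or their analysis.

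**What to change.** **Testing.** For every woman not exempt under 6.2.2, require a negative urine test shortly before the first dose of each course: on site, or by a supplied home kit with staff confirming the result before dosing when the visit is remote. Tie the requirement to the first dose rather than to the visit. Add it to 6.1 (Visits 1, 3 and 5, with a note on first-dose timing), 6.2.4 and 7.2. State that home testing is allowed, since 6.2.2 and 6.2.4 currently list the test among the Baseline procedures that cannot be done virtually.

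**Visit 1 limit.** State one limit in 6.2.2 and 6.2.4, and align the screen-fail and rescreening sentences with it. Fourteen days is the stricter choice and fits the stated 9 + 2 weeks if these are counted from Baseline (77 days). If 30 days is kept, section 3 should say that its duration runs from Visit 1.

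**Cost.** At most 3 × 31 = 93 urine tests (fewer with exemptions), the home kits, a brief remote contact when the first dose falls after the visit, and the wording. No extra in-person visit is needed, and endpoints and blinding are unaffected.
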